6.1.8. Use of an Efficacy Subset of Subjects

Subjects included in the Per Protocol (PP) Population will be included as a subset of the ITT population. Any major protocol deviations will be defined at the time of evaluability evaluation, prior to unblinding.

Excluding subjects who have major protocol deviations is expected to decrease the number of variables impacting the treatment response.

6.1.9. Examination of Subgroups

Descriptive summaries on the primary and secondary endpoints using the ITT population will be included for the following subgroups of gender, age, ethnicity, and race. Age will be summarized as categories of < 18 years, ≥ 18 to < 65 years, and ≥ 65 years.

6.2. Disposition of Subjects

The number of subjects included in each analysis population (ITT and PP) will be summarized by treatment group.

The number of subjects enrolled, completed, and discontinued (including the reasons for discontinuation) will be summarized for each treatment group by each analysis population.

The ear being treated (Left, Right, Both) will be summarized by treatment group.

Subjects who are excluded from an analysis population will be summarized by the reason for exclusion based on primary reason for exclusion.

6.3. Protocol Deviations

Protocol deviations will not be entered into the database. Deviations leading to exclusion from analysis populations will be identified before database lock. Protocol deviations will be presented in a by-subject listing.

6.4. Analysis Populations

Subjects will be presented/summarized based on the primary reason for exclusion. The primary reason for exclusion for each population will be assigned based on the order presented in each section below.

6.4.1. Intent-to-Treat (ITT) Population

All subjects who were randomized and dispensed study drug will be included in the ITT population and analyzed according to the treatment group into which they were randomized.

All efficacy analyses will be presented using the ITT population.

6.4.2. Per Protocol (PP) Population

The PP population will be a subset of the ITT population and will include all subjects who complete the Test of Cure visit without any major protocol violations and analyzed according to the treatment each subject actually received. The PP population will include subjects in the ITT population who did not meet any of the following criteria:

- Violated the inclusion/exclusion criteria
- Used an interfering concomitant medication
- Did not attend the Test of Cure visit
- Did not attend the End of Treatment visit
- Have not been compliant with the dosing regimen (i.e., subjects must have received 80% 120% of the expected doses of study medication in the study ear during participation in the study)
- Out of visit window at the Test of Cure Visit (-1/+8 days)
- Missed Test of Cure Visit signs and symptoms

Subjects who discontinue from the study due to an adverse event (AE) related to study treatment, documented lack of treatment effect, or worsening of condition will be included in the PP population. Prior to breaking the blind, other additional criteria may be added to the list to accommodate for unforeseen events that occurred during the conduct of the trial that result in noteworthy study protocol violations.

Efficacy analyses performed using the PP population will be in a supportive manner.

6.4.3. Safety Population

The Safety population will include all subjects who received at least one dose of study drug and had at least one post-Baseline safety assessment.

All safety analyses will be performed using the Safety population and analyzed according to the treatment each subject actually received.

6.5. Demographic and Other Baseline Characteristics

Subject demographic and baseline characteristics will be summarized descriptively by treatment for the ITT, PP and safety populations. Demographic data will also be listed.

Sex, race, and ethnicity will be summarized by counts and percentages. Age will be summarized with descriptive statistics and categorically (< 18 years, ≥ 18 to < 65 years, and ≥ 65 years) for subgroup analyses.

Medical histories will be coded using the Medical Dictionary for Regulatory Activities (MedDRA) dictionary and presented in a by-subject listing.

6.6. Prior and Concomitant Medications

Concomitant medications will be coded to preferred name and Anatomical Therapeutic Chemical (ATC) classification of ingredients using the World Health Organization (WHO) Drug dictionary (WHO-DDE).

Medications which start prior to first dose will be considered prior medications. Ongoing medications and medications ending after the date of first dose will be considered concomitant medications. Medications which are both prior and concomitant will be included in both summaries. Incomplete start and end dates which could be either prior to first dose or after first dose will be considered prior to first dose.

A by-subject listing of all prior and concomitant medications and procedures/therapies will be presented.

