2.3 Primary Estimand

The primary estimand will address the following clinical question of interest:

- To establish the efficacy of miconazole oil when taken over a 14-day treatment duration compared with mineral oil in subjects with uncomplicated otomycosis of the external ear only.

This primary estimand is defined as follows:

- Target population: all randomized subjects as defined by the study inclusion / exclusion criteria who are dispensed study drug (ITT population).
- Variable of interest (primary efficacy endpoint): the proportion of subjects who achieve Clinical Cure, defined as score of 0 for fungal elements, and 0 for each of the signs/symptoms of pruritus, aural fullness and debris at the Test of Cure visit
- Intercurrent events (IcE)
 1. Discontinuation of study treatment due to AE unrelated to study drug
 2. Discontinuation of study treatment due to AE related to study drug
 3. Discontinuation of study treatment due to lack of efficacy
 4. Use of rescue medication prior to the Test of Cure visit

For each above IcE, a composite strategy will be taken where subjects with any of the above IcEs will be considered to have not achieved Clinical Cure.

- Population-level summary: the difference in proportions in Clinical Cure at the Test of Cure visit between the miconazole group and the mineral oil group.

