5.2 Prohibited Medications

Other than the study drug, no other topical medications are allowed to be used in any ear that is being treated with study drug. Other prohibited treatments during the study include systemic antifungal therapy, warfarin, immunosuppressive or immune-stimulating drugs, antibiotics, and systemic steroids.

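### SAP 6.6 sets an ambiguous incomplete end date to before first dose, so a drug used on study can be classed as prior only and missed in the concomitant summary and possibly in the per protocol review

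*SAP*

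**What the plan says.** SAP 6.6 defines the two classes separately. On prior use: "Medications which start prior to first dose will be considered prior medications". On concomitant use: "Ongoing medications and medications ending after the date of first dose will be considered concomitant medications". The classes may overlap: "Medications which are both prior and concomitant will be included in both summaries". The partial-date rule then covers both ends of a record: "Incomplete start and end dates which could be either prior to first dose or after first dose will be considered prior to first dose". Every record is kept in a listing: "A by-subject listing of all prior and concomitant medications and procedures/therapies will be presented".

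Three other places bear on the consequences:

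- SAP 6.4.2 removes a subject from the per protocol (PP) population for having "Used an interfering concomitant medication". It does not define interfering and does not refer to SAP 6.6.
- Protocol 5.2 states that, apart from study drug, "no other topical medications are allowed to be used in any ear that is being treated with study drug". It also bars systemic antifungals, warfarin, immune-modifying drugs, antibiotics and systemic steroids during the study.
- Protocol 2.3 lists "Use of rescue medication prior to the Test of Cure visit" as an intercurrent event under a composite strategy. SAP 6.7.1 replaces this with treatment policy, on the ground that rescue medication is not specifically defined.

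**The concern.** Concomitant status depends on the end date. A rule that moves a doubtful end date to before first dose therefore takes that status away from a drug that may have been in use after dosing began. The doubt is settled in the direction that hides on-study use.

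The PP population is where this could matter for efficacy. Because the SAP takes rescue medication as recorded under treatment policy, and SAP 6.7.3 offers only the PP repeat as a sensitivity analysis, the interfering-medication criterion is the one planned efficacy rule that responds to use of another drug. It is worded with the term that SAP 6.6 defines. If the review takes the derived class at face value, a subject who took a prohibited drug during the study could stay in the PP set. The concomitant medication summary would be short by the same records.

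**Working it through.** The plan gives no figure to reproduce. The check applies the rule to each feasible pattern of dates.

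**Step 1. Classification under SAP 6.6 as written.** Illustrative first dose on 10 March; month-only means that just March and the year are recorded.

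| Start date | End known, before dose | End known, after dose | Ongoing | End month-only |
|---|---|---|---|---|
| Known, before dose | prior | prior and concomitant | prior and concomitant | **prior only** |
| Known, after dose | not possible | concomitant | concomitant | **neither** (literal reading) |
| Month-only | prior | prior and concomitant | prior and concomitant | **prior only** |

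Of the 11 feasible patterns, concomitant status is lost through the rule only in the three with a month-only end. The month-only start does no such damage: with a known post-dose end, or ongoing use, the drug stays concomitant. The cell marked neither arises only if the rule is applied without thought, since a drug cannot end before a known post-dose start. That leaves two real problem patterns: an ambiguous end date with a start that is before dose or is itself ambiguous.

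**Step 2. How often a month-only end date would be ambiguous.** Assume that first-dose dates and true end dates are spread evenly over the calendar. Over two years including one leap year the mean month length is 731/24 = 30.46 days. For an end date k days after Day 1, with k shorter than a month, the chance of the same calendar month is 1 − k/30.46. Averaging over k:

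- End on Days 2 to 22 (k = 1 to 21, mean 11): 1 − 11/30.46 = 0.64
- End on Days 2 to 14 (mean 7): 1 − 7/30.46 = 0.77
- End on Days 2 to 25 (mean 12.5): 1 − 12.5/30.46 = 0.59

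When first dose falls on the first of a month, an end date in that month cannot be before dosing, so it is not ambiguous. This takes off 24/731 = 0.03, leaving about 0.61, 0.74 and 0.56. A year-only end date on Days 2 to 22 falls in the same year with chance 1 − 11/365.5 = 0.97.

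These shares are conditional on an incomplete end date and a start that is before dose or ambiguous. The documents do not say how many such records to expect, so no number of subjects follows.

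**Step 3. Whether the eligibility criteria catch the drug anyway.** A drug placed before first dose by the rule ended in the same calendar month as dosing, hence at most d − 1 days earlier when first dose is on day d. Compare Protocol 4.2 with Protocol 5.2:

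- Systemic antifungals, warfarin and immune-modifying drugs have a 28-day limit. The drug is inside it whenever d − 1 ≤ 28, that is, on all but the last days of a long month.
- Systemic steroids have a 3-month limit: always inside.
- Topical otomycosis treatments have a 14-day limit: certainly inside when d ≤ 15, otherwise not certain.
- Antibiotics are barred on study but have no washout of their own. Protocol 4.2 reaches them only through otic infections that need antimicrobial treatment.
- Other topical products in a treated ear are barred on study, but the washout covers only those used for otomycosis.

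In the first three groups the subject would often leave the PP set for an eligibility breach instead, though under the wrong reason. The last two groups can pass unnoticed.

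**The case against.** The strongest reply is that nothing ties the PP criterion to the derived class. SAP 6.6 serves summaries and listings. SAP 6.1.8 and 6.3 have major deviations settled before unblinding and exclusions identified before database lock, and the listing shows every medication whatever its label. Protocol 7.12 has the investigator document the date and nature of each deviation. Medications are reviewed at all three visits, a change of therapy is generally reported with an adverse event that carries an onset date, and Protocol 11.6 requires discrepant entries to be queried. This stands: the PP consequence is possible, not stated. What remains is that SAP 6.4.2 uses the word that SAP 6.6 defines and does not say that the reviewers may look past the label.

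Three stronger readings are tempting:

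- A reader might infer that any drug possibly taken after first dose becomes prior. The table shows otherwise: ongoing drugs and those with a known post-dose end date stay concomitant whatever the start date.
- A reader might infer from Protocol 2.3 that hidden rescue use turns failures into cures in the primary analysis. Under SAP 6.7.1 rescue use does not alter the recorded outcome, so the ITT result is the same either way. The difference between protocol and SAP on rescue is a separate matter. Neither document plans a count of rescue use that could come out too low.
- A reader might take the share of about 61% as the size of the harm. It describes only records that already have an incomplete end date.

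**Conclusion.** The end-date half of the SAP 6.6 rule gives a wrong classification for a drug used on study whose end date is incomplete and ambiguous and whose start is before dose or also ambiguous. The certain effect is an undercount in the concomitant medication summary. The conditional effect, if the PP review relies on the label, is missed prohibited use in a supportive analysis, chiefly of antibiotics and of topical ear products not given for otomycosis. The primary ITT analysis does not change.

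The point is minor. In so short a study a month-only end date would usually be ambiguous (roughly 56% to 74% over the ranges above, with dates spread evenly). The number of incomplete end dates is unknown, and visit-by-visit recording makes it likely to be small.

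**What to change.** Keep the present rule for incomplete start dates. Replace the end-date part of SAP 6.6 with:

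*An incomplete end date that could be before or after first dose is considered to be after first dose, so the medication is concomitant, unless the known parts of the date show that it ended before first dose.*

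Add to SAP 6.4.2:

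*Interfering medication is judged before unblinding from the full by-subject medication listing, not from the derived prior/concomitant flag alone.*

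The first sentence changes only the month-only-end column of the table: those three patterns become concomitant, and no other pattern moves. Its cost is that a few truly prior medications will also appear in the concomitant table. The second sentence is needed because applying the new label mechanically to the PP set could exclude subjects whose drug had in fact stopped before dosing. It adds a short case review to the evaluability assessment already planned. Both changes should be made before unblinding.

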6.7. Analysis of Efficacy

6.7.1. Primary Efficacy Analysis

The primary population for efficacy analyses will be the ITT population. Efficacy analyses will also be performed on the PP population and will be considered supportive.

The primary estimand will address the following clinical question of interest:

- To establish the efficacy of miconazole oil when taken over a 14-day treatment duration compared with mineral oil in subjects with uncomplicated otomycosis of the external ear only.

This primary estimand is defined as follows:

- Target population: all randomized subjects as defined by the study inclusion / exclusion criteria who are dispensed study drug (ITT population).
- Variable of interest (primary efficacy endpoint): the proportion of subjects who achieve Clinical Cure, defined as score of 0 for fungal elements, and 0 for each of the signs/symptoms of pruritus, aural fullness and debris at the Test of Cure visit
- Intercurrent events (IcE)
 1. Discontinuation of study treatment due to AE unrelated to study drug
 2. Discontinuation of study treatment due to AE related to study drug

3. Discontinuation of study treatment due to lack of efficacy, as defined by 'withdrawal by subject' as primary reason for study discontinuation.
4. Use of rescue medication prior to the Test of Cure visit

For IcEs above 1-3, a composite strategy will be taken where subjects will be considered to have not achieved Clinical Cure. For IcE 4, since rescue medication is not specifically defined, a treatment policy strategy will be taken; the data will be used as recorded regardless of other medication. Additionally, any IcEs not explicitly defined here which result in missing data which have not been specified are treated in the same way; missing data at the Test of Cure visit will be considered as not achieving Clinical Cure.

- Population-level summary: the difference in proportions in Clinical Cure at the Test of Cure visit between the miconazole group and the mineral oil group.

The number and percentage of subjects with Clinical Cure at the Test of Cure Visit will be presented.

The primary analysis of Clinical Cure at the Test of Cure Visit will test the following hypothesis:

H0: $p_T - p_P = 0$

H1: $p_T - p_P \neq 0$

where H0 is the null hypothesis, H1 the alternative hypotheses, and p_T and p_P are percentage of subjects with success for Clinical Cure in the Treatment (miconazole oil) and Placebo (mineral oil) groups, respectively. Comparisons between groups for the difference in the percentage of subjects achieving the primary endpoint of Clinical Cure at the Test of Cure visit will be conducted using a Cochran-Mantel-Haenszel (CMH) test stratified by analysis center with a 2-sided significance level of 0.05.

For subjects with bilateral otomycosis in which at least one ear meets all study eligibility criteria, both ears may be treated with study drug provided that both ears have a score of 1 for fungal elements, and the determination of the study ear will be made as described in Section 4.1.

Primary efficacy endpoints will also be presented in a by-subject listing including each component of Clinical Cure and response.

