4.4 Subject Discontinuation

A subject MAY be withdrawn from the study (at the discretion of the investigator, sponsor, and/or IRB) prior to study completion for any of the following reasons, including, but not limited to:

- A serious adverse event (SAE) occurring during the course of the study which precludes continued follow-up
- Intercurrent illness which may, in the investigator's opinion, significantly affect study assessments
- Failure to follow required study procedures

A subject MUST be discontinued prior to the final study visit for any of the following reasons:

- Whenever the subject decides it is in his/her best interest to withdraw

- Whenever the investigator decides it is in the subject's best interest to be withdrawn

Prior to discontinuing a subject, every effort should be made to contact the subject, schedule a final study visit, and obtain as much follow-up data as possible. If possible, the assessment schedule for the Test of Cure Visit should be performed, and an effort should be made to collect all study drug.

Subject discontinuations will be documented clearly on the applicable electronic case report form (eCRF).

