6.7.2. Secondary Efficacy Analysis

The secondary endpoints will be analyzed analogously to the primary endpoint, including the treatment of IcEs and missing data.

- Modified Clinical Cure at the Test of Cure visit
- Clinical Clearance at the Test of Cure visit
- Modified Clinical Cure at the End of Treatment visit
- Clinical Clearance at End of Treatment visit
- Clinical Cure at the End of Treatment visit

A stepwise process will be conducted for testing the secondary efficacy endpoints in order to control for multiplicity; refer to [Section 6.1.7.](#)

All secondary efficacy analyses will be presented using the ITT population. Analyses will also be presented in a supportive manner using the PP population. All efficacy data will be included in by-subject listings.

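### SAP 6.7.1 detects stopping treatment for lack of efficacy by 'withdrawal by subject' from the study, which is a different event from the one it names and from Protocol 2.3

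*SAP*

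**What the plan says.** Protocol 2.3 lists "Discontinuation of study treatment due to lack of efficacy" among four intercurrent events and does not say how it is to be identified. For all four, "a composite strategy will be taken where subjects with any of the above IcEs will be considered to have not achieved Clinical Cure".

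SAP 6.7.1 keeps the event but adds an operational definition: "Discontinuation of study treatment due to lack of efficacy, as defined by 'withdrawal by subject' as primary reason for study discontinuation". The strategy is then "For IcEs above 1-3, a composite strategy will be taken where subjects will be considered to have not achieved Clinical Cure". For rescue medication the SAP departs from the protocol: "a treatment policy strategy will be taken; the data will be used as recorded regardless of other medication". Missing Test of Cure data count as non-cure whatever the cause.

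SAP 6.7.2 carries these rules over: "The secondary endpoints will be analyzed analogously to the primary endpoint, including the treatment of IcEs and missing data". Three of the five secondary endpoints are assessed at End of Treatment, and they hold the last three places in the testing order of SAP 6.1.7.

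SAP section 8 says only that intercurrent events are given in more detail than in the protocol. It does not mention a changed definition.

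**The concern.** The SAP wording makes two substitutions: leaving the study stands in for stopping the drug, and the subject's own decision stands in for lack of efficacy. The documents elsewhere keep these apart.

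- Protocol 4.4 requires discontinuation "Whenever the subject decides it is in his/her best interest to withdraw", which covers any personal reason.
- Protocol 8.5 allows a pregnant subject to come off study drug and remain in the study. Protocol 8.4 records permanent discontinuation of drug as an action in its own right.
- SAP 6.4.2 says that subjects who discontinue for "documented lack of treatment effect, or worsening of condition will be included in the PP population". It therefore treats lack of effect as a reason of its own, not as a form of subject withdrawal.

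A programmer following SAP 6.7.1 would flag a different set of subjects from the set Protocol 2.3 describes. Since flagged subjects are scored as non-cures, the error can run both ways: a true event goes uncounted, or an observed cure is overwritten.

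**Working it through.** **Which subjects change.** Compare the event as named in Protocol 2.3 with the flag in SAP 6.7.1, then apply the remaining SAP rules.

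| Subject | Named event occurred? | SAP flag? | Does the result change? |
|---|---|---|---|
| A. Stops drug as ineffective, no AE, stays, still symptomatic at Test of Cure | Yes | No | No: non-cure on observed scores |
| B. As A, but all four scores 0 at Test of Cure | Yes | No | Yes: cure under the SAP, non-cure under Protocol 2.3 |
| C. Stops drug because symptoms worsen, reported as an AE (Protocol 8.1) | Caught as IcE 1 or 2 | Not needed | No: non-cure |
| D. Withdraws for unrelated reasons, no Test of Cure data | No | Yes | Not at Test of Cure: non-cure by the missing-data rule |
| E. Withdraws for unrelated reasons, early-termination scores all 0 on days 19 to 30 (mapped to Test of Cure by SAP 6.1.2) | No | Yes | Yes: an observed primary-endpoint cure becomes a failure |
| F. Completes 14 days, cured at End of Treatment, withdraws before Test of Cure for unrelated reasons | No | Yes | Test of Cure: no (missing). End of Treatment: yes, through SAP 6.7.2 |

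A subject whom the investigator takes out for lack of effect is not coded as withdrawing by choice, so the flag misses that subject too. The outcome then follows A or B if scores exist, and is non-cure if they are missing.

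Only B, E and F change a result. B and E touch the primary endpoint. F touches the three End of Treatment endpoints and is the clearest case: a subject who finished the course cannot have discontinued treatment.

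**Size per subject.** With 55 per group (SAP section 7), one subject is 1/55 = 1.8 percentage points.

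**The plan's design figure.** The plan attaches no number to this rule. Its only design figure is about 80% power for 35% against 10% with 55 per group. Exact enumeration gives 85.5% for Fisher's test and 90.5% for the uncorrected chi-square, so the stated figure is not reproduced but is conservative. It is used here only as a baseline.

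**Illustration, with the number of affected subjects k assumed.** The expected cures are 0.35 × 55 = 19.25 and 0.10 × 55 = 5.5.

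- Case B, k mineral-oil subjects scored as cured: control rate (5.5 + k)/55. For k = 0, 1, 2, Fisher power is 85.5%, 77.7%, 68.5%, and chi-square power 90.5%, 84.1%, 76.0%.
- Case E, k cured miconazole subjects scored as failures: active rate (19.25 − k)/55. For k = 0, 1, 2, Fisher power is 85.5%, 80.2%, 73.7%, and chi-square power 90.5%, 86.6%, 81.7%.

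**Effect on a single result** (unstratified chi-square; z = (x − y)/55 divided by √[p̄(1 − p̄) × 2/55], with p̄ = (x + y)/110):

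- 19 against 6 cures: p̄ = 25/110, z = 2.96, p = 0.003. 19 against 7: p̄ = 26/110, z = 2.69, p = 0.007.
- 19 against 9 cures: p̄ = 28/110, z = 2.19, p = 0.029. 19 against 10: p̄ = 29/110, z = 1.95, p = 0.052.

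Near the planned control rate one subject does not alter the conclusion. It does so only near the boundary, here at control rates of 9/55 = 16% to 10/55 = 18%. The planned test is a CMH test stratified by analysis center, so these p-values are indicative only.

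**The case against.** The strongest case against is that other rules already do most of the work. Missing Test of Cure data are failures, so most subjects who withdraw early fail with or without IcE 3. Subjects for whom the drops do not work will mostly still be symptomatic at Test of Cure. Worsening or recurrence of symptoms must be reported as an AE, so many efficacy-related stops fall under IcE 1 or 2. In the previous Phase 3 study, fungal ear infection led to discontinuation in 2 of 88 miconazole and 6 of 89 vehicle subjects (Protocol Table 4). All of this stands, and it confines the primary-endpoint effect to cases B and E. It does not cover a subject who simply fails to improve, stops, and has no AE.

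It can also be said that case F never meets the opening words of IcE 3, because treatment was completed. That is a sensible reading, but the SAP says the event is defined by the withdrawal code, and a program will use the code.

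A reader might infer that a subject who abandons the drug, uses another antifungal and is clear at Day 22 counts as a success because of this definition. That result rests mainly on the separate SAP rule for rescue medication, which differs from Protocol 2.3 and must be reconciled in its own right. Protocol 5.2 also prohibits such use, and SAP 6.4.2 removes users of interfering medication from the per-protocol analysis.

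Finally, the eCRF is not among the documents. The proxy may reflect what was collected, and a reference to documented lack of effect does not prove that a separate reason for stopping drug is recorded.

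**Conclusion.** The definition is wrong as written: it identifies neither the event it names nor the one in Protocol 2.3, and no other rule repairs it. It should be corrected, but the consequence is limited. For the primary endpoint it matters only for cases B and E. That effect is probably small and cannot be computed, because the documents give no count of such subjects; what can be said is 1.8 points per reclassified subject in an arm of 55. The clearest harm is to the three End of Treatment secondary endpoints, where an observed cure can be overwritten by a later, unrelated withdrawal.

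Two stronger readings are not supported. A reader might infer that the composite strategy fails altogether. It does not: IcEs 1 and 2 and the missing-data rule are unaffected, and the proxy does catch a subject who leaves the study because the drug does not work, if coded that way. A reader might also infer from the move from p = 0.029 to p = 0.052 that one subject is likely to decide the trial. Those counts assume a control cure rate well above the planned 10%; near the planned rate the move is from 0.003 to 0.007.

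**What to change.** 1. In SAP 6.7.1, define IcE 3 by the recorded reason for stopping study drug (lack of efficacy or worsening), whether or not the subject stays in the study.
2. Handle 'withdrawal by subject' only through the missing-data rule.
3. In SAP 6.7.2, state that for End of Treatment endpoints only intercurrent events before that assessment count.
4. Reconcile the definition with Protocol 2.3 and list any remaining difference in SAP section 8.

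The cost is SAP wording if the eCRF already records why drug was stopped separately from why the subject left the study. If it does not, one reason field is needed. If that cannot be added, the minimum is not to apply the proxy to subjects who completed treatment, nor to assessments made before the withdrawal. That protects observed cures (case F, and case E where treatment was completed or the assessment came before the withdrawal) but leaves case B uncorrected, which the SAP should then acknowledge.
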